# **MODIFICATION HISTORY**

Unique	Date of the		
Identifier for	Document		Significant Changes from
this Version	Version	Author	Previous Authorized Version
V1.0	12AUG2019	[name]	N/A

Document: PK/PD STATISTICAL ANALYSIS PLAN

Author: [name] Version Number:

Version Date: 12 Aug 2019

1.0

Template No: CS\_TP\_BS016 – Revision 5 Reference: CS\_WI\_BS005

Effective Date: 01Apr2018

Palladio BiosciencesInsert Customer Name/ Logo PK/PD STATISTICAL ANALYSIS PLAN: PROTOCOL PA-102 Page 4 of 39

### **LIST OF ABBREVIATIONS**

Abbreviation	Definition
ADPKD	autosomal dominant polycystic kidney disease
AE	adverse event
AM	morning
AUC	area under the plasma concentration-time curve
AUC (0-14)	area under the plasma concentration-time curve from time 0 until 14 hours post-dose
AUC (0-inf)	area under the plasma concentration-time curve extrapolated to infinity
AUC(0-last)	area under the plasma concentration-time curve from time 0 until the last quantifiable concentration
BID	twice daily
BLQ	below the lower limit of quantification
CKD	chronic kidney disease
CKD1	chronic kidney disease stage 1
CKD2	chronic kidney disease stage 2
CKD3	chronic kidney disease stage 3
CL/F	apparent systemic clearance after extravascular dosing
$C_{max}$	maximum observed plasma drug concentration
CSR	clinical study report
CV	coefficient of variation
eGFR	estimated glomerular filtration rate
N	sample size
n	number of non-missing observations
PD	pharmacodynamic(s)
PK	pharmacokinetic(s)
PM	evening
SAP	statistical analysis plan
SD	standard deviation
$t_{1/2}$	terminal elimination phase half-life
$t_{max}$	time to reach maximum plasma concentration
$V_z/F$	apparent volume of distribution after extravascular dosing
$\lambda_{ m Z}$	apparent terminal elimination rate constant

Document: PK/PD STATISTICAL ANALYSIS PLAN

Author: [name] Version Number:

Version Date: 12 Aug 2019

1.0

Template No: CS\_TP\_BS016 – Revision 5 Reference: CS\_WI\_BS005

Effective Date: 01Apr2018

Palladio BiosciencesInsert Customer Name/Logo PK/PD STATISTICAL ANALYSIS PLAN: PROTOCOL PA-102 Page 8 of 39

### 1. Introduction

This document describes the rules and conventions to be used in the presentation and analysis of pharmacokinetic (PK) and pharmacodynamic (PD) data for Protocol PA-102. It describes the data to be summarized and analyzed, including specifics of the statistical analyses to be performed. This statistical analysis plan (SAP) is based on protocol version 5, dated 21 March 2019. The analysis and presentation of the data not related to PK or PD are described in an analysis plan (dated 25 April 2019) referred to as the "Non-PK/PD SAP" in this document.

### 2. STUDY OBJECTIVES

#### 2.1. **PRIMARY OBJECTIVE**

The primary objectives of this study are:

- To characterize the safety and tolerability of lixivaptan following multiple doses in autosomal dominant polycystic kidney disease (ADPKD) subjects with relatively preserved kidney function (chronic kidney disease stage 1 [CKD1] and stage 2 [CKD2]) and moderately impaired renal function [CKD3].
- To characterize the PK profile of lixivaptan and its major metabolites (WAY-141624, WAY-138451, and WAY-138758) following multiple doses of lixivaptan in ADPKD subjects with relatively preserved kidney function (CKD1 and CKD2) and moderately impaired renal function (CKD3).

PK/PD STATISTICAL ANALYSIS PLAN Document:

Author: [name] Version Number: Version Date: 12 Aug 2019

1.0

Template No: CS\_TP\_BS016 - Revision 5 Reference: CS\_WI\_BS005

Effective Date: 01Apr2018

Palladio BiosciencesInsert Customer Name/ Logo PK/PD STATISTICAL ANALYSIS PLAN: PROTOCOL PA-102 Page 9 of 39

# 2.2. SECONDARY OBJECTIVES

The secondary objectives of this study are:

- To characterize the effect of lixivaptan on urine osmolality over a 24-hour period following multiple doses of lixivaptan in ADPKD subjects.
- To characterize the time course of the pharmacodynamic effect of lixivaptan on urine output, total kidney volume, liver volume, plasma copeptin, and serum creatinine in ADPKD subjects.

### 3. STUDY DESIGN

### 3.1. GENERAL DESCRIPTION

This is a Phase 2, open-label, parallel-group, multiple dose study designed to evaluate the PK, PD, safety and tolerability of multiple twice daily (BID) doses of 50 mg and 200 mg lixivaptan in ADPKD subjects with chronic kidney disease in stages CKD1, CKD2 or CKD3. Enrolled subjects will be assigned according to CKD classification to take one of 2 lixivaptan oral dose regimens for 7 days as shown below (Table 1). Each dose regimen includes morning (AM) and evening (PM) oral administration of lixivaptan.

Table 1 Chronic Kidney disease Classification Summary by Cohort and Dose Group

CKD Stage	Cohort	N	eGFR a	Dose
CKD1 or CKD2	1	8	eGFR $\geq$ 60 mL/min/1.73 m 	200 mg BID
CKD3	2	8	eGFR $\geq$ 30 to < 60 mL/min/1.73 m 	200 mg BID
CKD1 or CKD2	3	8	eGFR $\geq$ 60 mL/min/1.73 m 	50 mg BID
CKD3	4	8	eGFR $\geq$ 30 to < 60 mL/min/1.73 m 	50 mg BID

Document: PK/PD STATISTICAL ANALYSIS PLAN
Author: [name]

Version Number: Version Date:

1.0 12 Aug 2019

Template No: CS\_TP\_BS016 - Revision 5

Effective Date: 01Apr2018

Reference: CS\_WI\_BS005

Palladio BiosciencesInsert Customer Name/ Logo PK/PD STATISTICAL ANALYSIS PLAN: PROTOCOL PA-102 Page 10 of 39

Abbreviations: CKD=chronic kidney disease; eGFR=estimated glomerular filtration rate; BID=twice daily.a eGFR is calculated by the 2009 Chronic Kidney Disease Epidemiology Collaboration (CKD-EPI) equation.

### 3.2. SCHEDULE OF EVENTS

Schedule of events can be found in Section 12.2 of the protocol.

# 3.3. CHANGES TO ANALYSIS FROM PROTOCOL

Some safety and/or PD endpoints were not clearly identified/categorized in the protocol. This SAP clarifies which endpoints are considered to be PD endpoints.

Some minor changes were made to some PK parameter abbreviations and/or definitions.

### 4. PLANNED ANALYSES

# 4.1. DATA MONITORING COMMITTEE

There is no Data Monitoring Committee for this study requiring statistical outputs.

### 4.2. INTERIM ANALYSIS

An interim "dry run" analysis is planned on partial data for this study to aid in preprogramming of databases and programs. However, only the results of the final analysis will be included in the clinical study report (CSR).

Document: PK/PD STATISTICAL ANALYSIS PLAN

Author: [name] Version Number: 1.0

Version Date: 12 Aug 2019

Template No: CS\_TP\_BS016 - Revision 5 Reference: CS\_WI\_BS005

Effective Date: 01Apr2018

Palladio BiosciencesInsert Customer Name/ Logo PK/PD STATISTICAL ANALYSIS PLAN: PROTOCOL PA-102 Page 11 of 39

# 4.3. FINAL ANALYSIS

All final, planned analyses identified in this SAP will be performed by IQVIA Biostatistics and PK scientist, following Palladio authorization of this SAP, identification of major protocol deviations/events requiring analysis exclusions, database lock, and determination of analysis sets.

### 5. ANALYSIS SETS

### 5.1. ALL SUBJECTS ENROLLED SET

The all subjects enrolled set will contain all subjects who provide informed consent for this study. Subjects in this population will be used for disposition summaries, and where appropriate, will be analyzed according to cohort allocation. Subjects not allocated to a cohort due to screen failure will be indicated as Not Allocated.

# 5.2. SAFETY ANALYSIS SET

The safety analysis set will contain all subjects who receive at least one dose of study medication and will be analyzed according to treatment received. This analysis set will be used for the safety analyses and for summarization of baseline/demographic characteristics, as well as listings of individual PK and PD data.

# 5.3. PHARMACOKINETICS ANALYSIS SET

The PK analysis set will consist of all subjects who undergo plasma PK sampling and have

Document: PK/PD STATISTICAL ANALYSIS PLAN

Author: [name] Version Number: 1.0

Version Date: 12 Aug 2019

Template No: CS\_TP\_BS016 - Revision 5 Reference: CS\_WI\_BS005

Effective Date: 01Apr2018

Palladio BiosciencesInsert Customer Name/ Logo PK/PD STATISTICAL ANALYSIS PLAN: PROTOCOL PA-102 Page 12 of 39

evaluable PK assay results, without protocol deviations or events deemed to affect PK evaluation. This analysis set will be used for the statistical analysis/summarization of PK concentration/parameter data and will be analyzed according to treatment received.

# 5.4. PHARMACODYNAMIC ANALYSIS SET

The PD analysis set will consist of all subjects who receive study drug and have at least one post-dose assessment of any PD endpoint, without protocol deviations or events deemed to affect PD evaluation. This analysis set will be used for the statistical analysis/summarization of PD data and will be analyzed according to treatment received.

# 6. GENERAL CONSIDERATIONS

Some minor modifications may be necessary to the planned design of tables, figures, and listings to accommodate data collected during the actual study conduct.

### 6.1. SUMMARY STATISTICS

For categorical variables, the analysis set size (N for sample size and n for number of non-missing observations) and percentage (of the number of non-missing observations) for each class of the variable will be presented. Percentages will be based on the number of subjects within the relevant analysis set and/or the number of subjects with non-missing observations. All continuous variables, except time to reach maximum plasma concentration ( $t_{max}$ ), will be summarized using descriptive statistics, including N, n, mean, standard deviation (SD), coefficient of variation (CV), median, minimum, and maximum values. The CV will not be presented for change from baseline results. Geometric mean and geometric CV will

Document: PK/PD STATISTICAL ANALYSIS PLAN

Author: [name] Version Number:

1.0 12 Aug 2019

Template No: CS\_TP\_BS016 – Revision 5 Reference: CS\_WI\_BS005

Effective Date: 01Apr2018

Copyright © 2009, 2010, 2012, 2016, 2018 IQVIA. All rights reserved. The contents of this document are confidential and proprietary to IQVIA Holdings Inc. and its subsidiaries. Unauthorized use, disclosure or reproduction is strictly prohibited.

Version Date:

Palladio BiosciencesInsert Customer Name/Logo PK/PD STATISTICAL ANALYSIS PLAN: PROTOCOL PA-102 Page 13 of 39

additionally be included for PK parameters, where applicable. The tmax will be summarized using descriptive statistics, including N, n, median, minimum, and maximum only.

For continuous variables, at least 3 (non-missing) observed values for each category will be required for calculation/presentation of descriptive statistics for that category. If n = 2, the 2 values will be presented as minimum and maximum, and no other descriptive statistics will be calculated. If n <2, only n will be reported. If n <2 for all categories for a summary, the summary table/figure may be omitted.

For categorical variables, no minimum number of observed values will be required for calculation/presentation of descriptive statistics (e.g., n and percentage).

#### 6.2. REFERENCE START DATE AND STUDY DAY

Study day will be calculated from the reference start date and will be used to show the start/stop day of assessments and events.

The reference start date is defined as the day of the first dose of study medication (Day 1 is the day of the first dose of study medication). Study day will be calculated relative to reference start date and will appear in every listing where an assessment date or event date appears.

- If the date of the event is on or after the reference date, then:
  - Study Day = (date of event reference date) + 1.
- If the date of the event is prior to the reference date, then:

Study Day = (date of event – reference date).

If the event date is partial or missing, the study day and any corresponding durations will be

PK/PD STATISTICAL ANALYSIS PLAN Document:

Author: [name] Version Number: 1.0 Version Date: 12 Aug 2019

Template No: CS\_TP\_BS016 - Revision 5 Reference: CS\_WI\_BS005

Effective Date: 01Apr2018

IMS Health & Quintiles are now

Palladio BiosciencesInsert Customer Name/ Logo PK/PD STATISTICAL ANALYSIS PLAN: PROTOCOL PA-102 Page 14 of 39

missing in the listings.

### 6.3. BASELINE

Unless otherwise specified, baseline is defined as the last non-missing measurement taken prior to start date of study drug administration (including unscheduled assessments). In the case where the last non-missing measurement and the start date of study drug administration coincide, that measurement will be considered pre-baseline.

# 6.4. RETESTS, UNSCHEDULED VISITS AND EARLY TERMINATION DATA

Post-baseline unscheduled measurements will not be included in summary statistics.

In the case of a retest of a scheduled assessment, the last available measurement for that scheduled time (i.e., the retest measurement) will be used for summaries unless flagged as invalid.

Listings will include all scheduled, unscheduled, retest and early discontinuation data.

### 6.5. WINDOWING CONVENTIONS

See Section 9.1.2 for handling specifications of data collected outside of protocol-specified windows.

Document: PK/PD STATISTICAL ANALYSIS PLAN

Author: [name] Version Number: 1.0

Version Date: 12 Aug 2019

Template No: CS\_TP\_BS016 - Revision 5 Reference: CS\_WI\_BS005

Effective Date: 01Apr2018

Palladio BiosciencesInsert Customer Name/ Logo PK/PD STATISTICAL ANALYSIS PLAN: PROTOCOL PA-102 Page 15 of 39

### 6.6. COMMON CALCULATIONS

For quantitative measurements, change from baseline will be calculated as:

• Test value (after baseline) – Baseline value

# 6.7. SOFTWARE VERSIONS

All derivations, statistical analyses, summaries, and listings will be generated using SAS version 9.4 (SAS Institute, Inc., Cary, North Carolina). Noncompartmental PK parameter calculations will be performed using Phoenix® WinNonlin® 8.0 or higher (Certara, Princeton, New Jersey). Graphics may be prepared using the same versions of SAS or Phoenix WinNonlin.

### 7. STATISTICAL CONSIDERATIONS

# 7.1. SAMPLE SIZE

Calculations to determine sample size were performed assuming a CV of 0.30 and 0.41 for lixivaptan maximum observed plasma drug concentration ( $C_{max}$ ) and area under the plasma concentration-time curve (AUC), respectively. Assuming a lognormal distribution, this implies that the variances for the logarithm of  $C_{max}$  and AUC are 0.086 and 0.155, respectively. Under these assumptions and a random sample of 8 observations per cohort, the probability is 0.90 that the point estimate of the population central value (observed geometric mean) for lixivaptan  $C_{max}$  and AUC will be within (84.3%, 118.6%) and (79.5%, 125.7%) of the population central value (the median), respectively.

From the perspective of tolerability assessment for multiple dose regimens, for the true

Document: PK/PD STATISTICAL ANALYSIS PLAN

Author: [name] Version Number: 1.0

Version Date: 12 Aug 2019

Template No: CS\_TP\_BS016 – Revision 5 Reference: CS\_WI\_BS005

Effective Date: 01Apr2018

Palladio BiosciencesInsert Customer Name/ Logo PK/PD STATISTICAL ANALYSIS PLAN: PROTOCOL PA-102 Page 16 of 39

population incidence rates of 0.10, 0.20, 0.30, 0.40 and 0.50 for a given adverse event (AE), the probabilities that the AE would not be observed in a group of 8 subjects administered lixivaptan are given in Table 2:

Table 2 Probability of Not Observing an Adverse Event for Various True Incidence Rates

True Incidence Rate	Probability of Not Observing an AE in Group of 8 Subjects
0.1	0.43
0.2	0.168
0.3	0.058
0.4	0.017
0.5	0.004

### 7.2. ESTIMANDS

As per International Council for Harmonisation E9 (R1), the estimands for this study are described as follows:

Primary Estimand 1: See Non-PK/PD SAP.

Primary Estimand 2: The PK profile of lixivaptan and its major metabolites (WAY-141624, WAY-138451, WAY-138758) following first and multiple doses of lixivaptan in ADPKD subjects.

- Population: ADPKD subjects with at least one post-dose PK assessment and defined further through appropriate inclusion/exclusion criteria.
- Variables (or endpoints): PK concentrations and parameters (Cmax, tmax, AUC from time 0 until the last quantifiable concentration [AUC(0-last)], AUC

Document: PK/PD STATISTICAL ANALYSIS PLAN

Author: [name] Version Number: 1.0

Version Date: 12 Aug 2019

Template No: CS\_TP\_BS016 - Revision 5 Reference: CS\_WI\_BS005

Effective Date: 01Apr2018

Palladio BiosciencesInsert Customer Name/ Logo PK/PD STATISTICAL ANALYSIS PLAN: PROTOCOL PA-102 Page 17 of 39

extrapolated to infinity [AUC(0-inf)], AUC from time 0 until 14 hours post-dose [AUC(0-14)], terminal elimination phase half-life [ $t_{1/2}$ ], apparent terminal elimination rate constant [ $\lambda_Z$ ], apparent systemic clearance after extravascular dosing [CL/F; lixivaptan only], and apparent volume of distribution after extravascular dosing [ $V_Z$ /F; lixivaptan only]).

- Strategy for addressing intercurrent event: Regardless if subject discontinues treatment prematurely.
- Population-level summary: Descriptive differences in PK parameter means of the four cohorts.

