1.7 Study Rationale

This study is being conducted to directly characterize the pharmacokinetic (PK), safety, and pharmacodynamic (PD) profiles of lixivaptan following administration of twice per day (BID) oral doses of 50 and 200 mg for 7 days in subjects with both autosomal dominant polycystic kidney disease (ADPKD) and chronic kidney disease (CKD) stage 1 (CKD1), stage 2 (CKD2) or stage 3 (CKD3). These proposed PK, safety, and PD assessments will be used to guide appropriate lixivaptan dosing recommendations for subjects with ADPKD and mild or moderate CKD.

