3.1.1 Rationale of Study Design

The I/E criteria in Section [4.1](#) were chosen to recruit an adequate number of subjects representative of the ADPKD population to achieve the study's primary objectives as presented in Section [2.1.1](#).

Based on existing clinical evidence with lixivaptan and the related vasopressin antagonist tolvaptan, the PK and PD properties of lixivaptan are not expected to differ in ADPKD subjects with CKD1 and CKD2 stages, therefore these subjects with relatively preserved kidney function will be combined into one study group. This approach decreases the total number of subjects that need to be recruited without compromising the study objectives. Conversely, subjects with moderately impaired renal function (CKD3 stage) may show distinct PK and PD responses to lixivaptan and will be enrolled into a separate group.

The PK profile of lixivaptan and its metabolites will be monitored for 3-5 half-lives after the last dose to define terminal PK parameters. Therefore, PK blood draws are included up to 96 hours, i.e. approximately 4 half-lives of the longest-lived metabolite of lixivaptan, after the last dose of lixivaptan (Day 7 PM).

Treatment with lixivaptan is associated with transient and reversible increases in serum creatinine and circulating vasopressin. In addition, based on clinical evidence with the related vasopressin antagonist tolvaptan,¹² lixivaptan may be associated with transient and reversible decreases in Total Kidney Volume (TKV). In order to characterize the time course and magnitude of these pharmacodynamic effects of lixivaptan in ADPKD subjects, the study design includes measurements of serum creatinine, plasma copeptin as a marker for circulating vasopressin, and TKV at three time points: at baseline, after completion of the scheduled treatment period and 4 weeks after the last dose of lixivaptan.

The sample size of 32 subjects in total, with 16 subjects per Cohort, is typical for this type of study and is considered adequate to meet the study objectives.

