7.4 Sample Size Calculations

Calculations were performed assuming a coefficient of variation (CV) of 0.30 and 0.41 for lixivaptan C_{max} and AUC, respectively. Assuming lognormal distribution, this implies that the variances for the logarithm of C_{max} and AUC are 0.086 and 0.155, respectively. Under these assumptions and a random sample of 8 observations, the probability is 0.90 that the point estimate of the population central value (observed geometric mean) for lixivaptan C_{max} and AUC will be within (84.3%, 118.6%) and (79.5%, 125.7%) of the population central value (the median), respectively.

From the perspective of tolerability assessment for multiple dose regimens, for the true population incidence rates of 0.10, 0.20, 0.30, 0.40 and 0.50 for a given AE, the probabilities that the AE would not be observed in a group of 8 subjects administered lixivaptan are given in [Table 7-1](#).

Table 7-1 Probability of Not Observing an Adverse Event for Various True Incidence Rates

True Incidence Rate	Probability of Not Observing an AE in Group of 8 Subjects
0.1	0.43
0.2	0.168
0.3	0.058
0.4	0.017
0.5	0.004

Abbreviation: AE = adverse event.

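### The primary PK summary is a difference between cohorts, but no between-cohort ratio or interval is prespecified for CKD3 versus CKD1/2

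*SAP*

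**What the plan says.** PK/PD SAP 7.2 (Primary Estimand 2) gives the population-level summary as "Population-level summary: Descriptive differences in PK parameter means of the four cohorts". The estimand covers lixivaptan and three metabolites.

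The sections that should deliver it contain the following:

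- **6.1 (Summary Statistics):** one-group statistics, with geometric mean and geometric CV added for PK parameters where applicable. For tmax, only median and range are planned, although tmax is among the estimand's variables.
- **6.6 (Common Calculations):** change from baseline only.
- **14.2 (Pharmacokinetic Parameters):** summaries by analyte, cohort, day and dosing interval, with further splits by sex and by CKD stage within cohort. Individual and geometric mean parameters are plotted against cohort for lixivaptan only. The ratios defined there are within-subject: Day 7/Day 1 accumulation and metabolite/parent.

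Protocol 3.1.1 explains that subjects with CKD3 "may show distinct PK and PD responses to lixivaptan and will be enrolled into a separate group". Protocol 1.7 says the PK, safety and PD assessments "will be used to guide appropriate lixivaptan dosing recommendations for subjects with ADPKD and mild or moderate CKD". The sample size text (Protocol 7.4, PK/PD SAP 7.1) addresses the precision of one cohort's geometric mean.

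**The concern.** The estimand names a difference between cohorts, but the analysis sections stop at describing each cohort. The arithmetic or geometric nature of the means is left open, as are the contrast, the day, the dosing interval and the AUC to be used.

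The renal comparison is the reason that half of the 32 subjects are recruited with CKD3. If two groups of 8 are set side by side without an interval, a chance difference can be read as an effect of renal function, or a real one can be passed over. Each dose level also carries information on the same renal ratio, and cohort-by-cohort tables leave that information uncombined.

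**Working it through.** **Inputs.** Protocol 7.4: "Calculations were performed assuming a coefficient of variation (CV) of 0.30 and 0.41 for lixivaptan" Cmax and AUC. PK/PD SAP 7.1: the log-scale variances for Cmax "and AUC are 0.086 and 0.155, respectively". There are 8 subjects per cohort, so 8 v 8 within a dose and 16 v 16 over both doses. No CV is given for any metabolite.

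**Step 1: reproduce the plan's figure.** Log variance = ln(1 + CV²): ln(1.09) = 0.0862 for Cmax and ln(1.1681) = 0.1554 for AUC. The 90% range for one cohort's geometric mean is exp(± 1.645 × √(variance/8)).

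- Cmax: 1.645 × √(0.086/8) = 0.1706, giving 84.3% to 118.6%.
- AUC: 1.645 × √(0.155/8) = 0.2290, giving 79.5% to 125.7%.

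The plan states that the estimate "will be within (84.3%, 118.6%) and (79.5%, 125.7%) of the population central value (the median), respectively", so its figures reproduce. They describe one cohort, as the text says: "random sample of 8 observations per cohort, the probability is 0.90 that the point estimate".

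**Step 2: precision of the renal ratio.** The 90% CI for a ratio of two geometric means is the estimate ×/÷ exp(t × √(2 × variance/n)), with n subjects per renal group.

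- Within one dose, n = 8, 14 df, t = 1.761.
- Both doses, n = 16, in a model with an intercept, renal group and dose: 32 − 3 = 29 df, t = 1.699.

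| Comparison | Parameter | √(2 × variance/n) | Factor | Multipliers on the ratio |
|---|---|---|---|---|
| 8 v 8 | Cmax | 0.1466 | 1.295 | 0.77 to 1.30 |
| 8 v 8 | AUC | 0.1969 | 1.414 (1.415 with the unrounded variance) | 0.71 to 1.41 |
| 16 v 16 | Cmax | 0.1037 | 1.193 | 0.84 to 1.19 |
| 16 v 16 | AUC | 0.1392 | 1.267 | 0.79 to 1.27 |

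**Step 3: what chance alone can produce.** Suppose there is no true renal effect, and a reader treats an observed ratio outside 0.80 to 1.25 as noteworthy. That band is an assumption for illustration; the documents set none. The probability is 2 × [1 − Φ(ln 1.25 / SE)], with SE from the table.

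- AUC, 8 v 8: 0.2231/0.1969 = 1.13, so about 26%. 16 v 16: 0.2231/0.1392 = 1.60, so about 11%.
- Cmax, 8 v 8: about 13%. 16 v 16: about 3%.

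With a wider assumed band of 0.67 to 1.50, the AUC figures fall to about 4% (0.4055/0.1969 = 2.06) and below 1% (0.4055/0.1392 = 2.91).

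**Step 4: whether an interval would be informative.** For an assumed true AUC ratio of 1.25, 1.5 or 2.0, the lower 90% limit would exceed 1 with probability 0.29, 0.62 or 0.96 for 8 v 8, and 0.47, 0.89 or 0.999 for 16 v 16. The intervals are wide, but combining the doses makes them usefully narrower.

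**The case against.** The case for leaving the plan as it is has real substance.

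- The summary is explicitly descriptive, and the primary objective is to characterise the PK profile in each renal group. Side-by-side tables are a legitimate, if weak, way to present descriptive differences. A reader might infer that nothing planned addresses the estimand, or that a hypothesis test is missing. The documents support neither reading.
- A reader might infer that the plan computes no ratios at all. It does: accumulation and metabolite/parent ratios are defined. What is absent is a ratio between cohorts.
- A reader might see a mismatch between sizing and analysis. There is none. The study is sized on each cohort's geometric mean, and that is what the tables report.
- An approximate ratio and interval could be rebuilt from the tabulated n, geometric mean and geometric CV. Protocol 7.1 also allows further calculations as appropriate.
- Protocol 1.7 does not say that a stage-specific dose will be set from this contrast.
- The output shells mentioned in PK/PD SAP section 8 are not among the documents reviewed, so a contrast shown only there cannot be excluded.

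All of this stands, and it limits the point to an improvement. It does not remove it. A ratio rebuilt afterwards leaves the parameter, day, dosing interval and pooling to be chosen once the data are known. The permission in Protocol 7.1 does not name a renal contrast. The metabolites, which belong to the same estimand, do not even get the scatter plot against cohort.

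**Conclusion.** The point holds in a limited form. The declared summary is a between-cohort difference, the SAP text prespecifies no between-cohort ratio or interval, and the type of mean is not stated. The planned tables remain valid, but they do not show the uncertainty of the CKD3 versus CKD1/2 comparison. That uncertainty is about ×/÷ 1.30 (Cmax) and ×/÷ 1.42 (AUC) within one dose, and about ×/÷ 1.19 and ×/÷ 1.27 over both doses, at 90% confidence.

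These figures rest on the plan's lixivaptan CVs, lognormal data, full cohorts of 8 and a common log variance. The pooled figures also assume a similar renal ratio at both doses. They do not require dose proportionality, because dose is a factor in the model. They cannot be carried over to the metabolites.

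It would go too far to say that an interval would establish a renal effect. Under Protocol 5.2, cohorts follow CKD status, the 200 mg cohorts are enrolled first, and the sex split may differ between cohorts. The interval addresses chance, not confounding.

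**What to change.** 1. **PK/PD SAP 7.2:** state the summary as the geometric mean ratio of CKD3 to CKD1/2, with 90% CI, for Cmax and AUC. Label it as estimation and not a test.
2. **PK/PD SAP 14.2:** add a linear model on ln(Cmax) and ln(AUC(0-14)) for the Day 7 PM dose, with renal group and dose as factors, fitted separately for lixivaptan and each metabolite. AUC(0-14) is already defined over a fixed interval for that dose. Naming it settles which of the Day 7 AUCs is meant.
3. **Same table:** report the ratio within each dose (8 v 8) beside the pooled ratio, so that the assumption of a similar renal ratio can be examined.
4. **State the limits in the text:** renal group is not randomised, the pooled ratio assumes a similar renal ratio and a common log variance at both doses, and the intervals will be wide.

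The cost is SAP wording and one added table. No new data, visits or subjects are needed. The only downside is that the intervals will be visibly wide, which is an honest picture of what 32 subjects can show.
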